- a) Levels of circulating pro-inflammatory biomarkers profiles (CRP, IL-6, TNF- α), NGAL (in urine), and lipid pro- and anti-inflammatory mediators (in plasma);
- b) Levels of coagulation biomarker and platelet function (e.g. fibrinogen, platelet counts, thrombomodulin, R, K, MA, G, angle, LYO)

Specific Aim 2: We will test the prediction that reduced post-surgical inflammatory burden of patients administered high-dose vitamin C will result in clinically significant reductions in hospital-based outcomes (such as length of hospital stay, length of ICU stay.)

STUDY DESIGN

This is a prospective, double-blind, placebo-controlled, randomized pilot trial comparing high-dose intravenous vitamin C to placebo (normal saline) infusions in elective non-emergent cardiac bypass patients. Double blinding will be used at enrollment, randomization, and throughout treatment, sampling, analysis, and data interpretation phases.

The purpose of this pilot study is to demonstrate **performance feasibility** and **proof of concept (PoC)** before initiation of a full-fledged clinical trial. Both financial and personnel constraints limit the total patient enrollment to 24 (12 per arm). Because sample sizes are so small, hypothesis testing cannot be a central feature of this proposal. Instead, success criteria will consist of tangible and measurable performance metrics relating to trial performance and PoC. *Performance success criteria* relate to the logistics and processes involved in the execution of the study itself (e.g. recruitment, retention, study flow, operations, management, obtaining samples, sample processing, documentation, compliance oversight). *Proof of concept* will be determined by large effect size differences (20%) between test and experimental intervention groups in one or more of the key inflammation and coagulation markers (see **OUTCOMES**).

It is unethical to consider running a phase III trial without sufficient data or feasibility information. This pilot trial will be extremely useful to inform the planning and execution of the future large-scale trial, especially with respect to feasibility and sample size calculations. Proof of concept information will be essential for writing major grants, which usually require such preliminary information for assessing scientific validity²¹⁻²³

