Dose/route. **Previous studies** describing use of IV vitamin C²⁴⁻²⁶ suggests that a total dose of 200mg/kg/day administered as 4 intravenous doses in 50mL D5W every 6 hours per day for 4 days will be sufficient to permit biologically-effective plasma concentrations, and thus are hypothesized to reduce deleterious effects associated with CPB-induced

November 16, 2016

inflammation. The intervention schedule in our study was based on a general knowledge of inflammation trajectory; inflammation typically peaks during CPB itself then stabilizes within a 24-hour period²⁷. **Accordingly, in this study** intravenous Vitamin C will be given as 200mg/kg/day divided over 4 intravenous doses every 6 hours per day for only 2 days perioperative.

Completion of study drug administration: Study drug administration will be stopped when one of the following conditions is met, whichever comes first:

1. Final drug dose at 48 hours
3. Inability to obtain peripheral access after removal of central line.
4. Discharge from the hospital
5. Withdrawal from study
6. Death

ETHICAL OVERSIGHT

Prior to study initiation, this study will be approved by the Virginia Commonwealth University (VCU) Institutional Review Board, and an IND requested from the Food and Drug Administration (FDA). The trial will be registered with *ClinicalTrials.gov*, and the definitive protocol submitted for publication in one of the open-access clinical trial specific journals (e.g. *Trials*). This is an investigator-initiated study, falling under an existing IND held by another investigator who is not acting as PI. In accordance with GCP, monitoring will occur through the use of a monitor not affiliated with this study. This monitor, while employed at the institution conducting the study, has not been affiliated with the development or execution of this study.

STUDY POPULATION

The study population will consist of adult patients scheduled for elective non-emergent cardiac surgery at Virginia Commonwealth University Medical Center, and who have consented to participation in the study.

Inclusion criteria are: (1) adult (≥ 18 years) patients (2) scheduled for elective non-emergent cardiac valve replacement or repair with cardiopulmonary bypass, and/or multi-vessel CABG surgery.

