This is a two-arm trial comparing high-dose IV vitamin C to normal saline placebo controls (Fig. 1). Once informed consent is obtained, the time of surgery will be communicated to the VCU investigational pharmacy so that the medication can be appropriately prepared and delivered to the operating room. Prior to preparation, patients will be randomized to receive either control or Vitamin C solution. Randomization will be performed by a computer-generated permuted block design conducted by the investigational pharmacy. Both test and placebo preparations will be prepared by pharmaceutical staff in identical de-identified 50-mL medication bags so as to be indistinguishable by OR/ICU staff and investigators.

Vitamin C will be administered in doses of 200 mg/kg/day group divided into four doses per day at six hour intervals 48 hours. Patients randomized to the control (normal saline) group will receive equivalent fluid volume in identical dispensing bags; total study fluid volumes will be approximately 400 mL over the two-day study period. Blinded interventions will be administered in the OR by the anesthesiologist, and post-operatively by Cardiac Surgery ICU nursing staff and/or Cardiac Stepdown Units. All participating hospital units will be provided with thorough in-servicing. Nurses will be prompted to administer the medication via the patient-specific electronic medical record (EMR).

OUTCOMES

Enrollment Goals: (1) Up to 40 may be enrolled in order to reach completion of 24 out of 24 subjects to allow for withdrawals; (2) complete follow-up and follow-up data for 24/24 (100%) of enrolled subjects; (3) all patients (24/24) to receive study drug according to randomization designation; (4) all patients (24/24) to receive every scheduled dose of the study drug in a blinded manner; (5) all patients (24/24) to have coagulation and biolipid determinations performed for all.

Biomarker outcomes:

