- Those receiving insulin infusion or sliding scale insulin will have metabolic glucose screening on the schedule determined by the primary physician and paid for by the study
- Blood glucose monitoring for insulin administration guidance should *only* be by a metabolic laboratory measured blood glucose results, whether or not the study patient is receiving insulin
- To accommodate the required glucose monitoring via the metabolic lab, each subject will have a dedicated peripheral line
- Study personnel will follow each study patient closely to monitor insulin use to ensure that point of care glucose screening is suspended for the research subject.
- If subject loses central venous access (PICC line and arterial line acceptable), Vitamin C infusions are to stop but subject not withdrawn. Data will be collected through end of study.
- Point of care glucose testing may resume 36 hours after the last infusion of study drug.

ADVERSE EVENT REPORTING/SAFETY REPORTING

Investigators will determine daily if any clinical adverse experiences occur during the period from informed consent through study hour 48 and will be followed up through resolution, resolved with sequelae, unresolvable or death.

It is expected that diseases/illnesses/symptoms associated with the study population will occur in the study population, independent of investigation product exposure. These associated diseases/illnesses/symptoms will be considered as part of the study inclusion processes and/or study assessments and as such will not be considered 'reportable' Adverse Events (AE)/Serious Adverse Events (SAE) unless the Investigator has a reasonable doubt regarding the relatedness of the event to the investigational product.

The investigator will evaluate any changes in laboratory values and physical signs and will determine if the change is clinically important and different from what is expected in the course of treatment of the study patients. If clinically important and unexpected adverse experiences occur, they will be recorded on the adverse event case report form.

The following will be considered reportable adverse events:

For this trial, a *reportable adverse event* is defined as:

November 16, 2016

1. Any clinically important untoward medical occurrence in a patient receiving study drug or undergoing study procedures which is different from what is expected in the clinical course of a patient undergoing cardiac bypass surgery, or,

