- Unexpected, in terms of nature, severity, or frequency, given the research procedures that are described in the protocol-related documents, such as the IRB-approved research protocol and informed consent document; and the characteristics of the subject population being studied;

November 16, 2016

- Related or possibly related to participation in the research. In this guidance document, possibly related means there is a reasonable possibility that the incident, experience, or outcome may have been caused by the procedures involved in the research;
- Suggests that the research places subjects or others at a greater risk of harm (including physical, psychological, economic, or social harm) than was previously known or recognized.

WITHDRAWAL CRITERIA

The Principal Investigator may withdraw the subject at any time due to subject failure to adhere to protocol, or for safety concerns.

TRIAL MANAGEMENT

It is expected that the trial will terminate when the intended sample size (24 patients) has been achieved. However, the trial will be stopped prior to completion if: (1) the intervention is associated with adverse effects that call into question the safety of the test intervention; (2) problems with study recruitment or retention will significantly impact the ability to evaluate the study endpoints; (3) any new information that becomes available during the trial necessitates discontinuation of the trial.

The trial protocol and results will be published in peer-reviewed journals. All publications will follow the Consolidated Standards for Reporting Trials (CONSORT) statement [25]. Credit for the study will be assigned to collaborators who have actually performed designated work. The results of the trial will be reported first to trial collaborators. Summary outcome data and links to published data will be uploaded to the *ClinicalTrials.gov* website.

ETHICAL CONSIDERATIONS

This research will involve the use of fresh blood drawn from patients. The blood draws will be done, when possible, from in-dwelling arterial line and central line catheters. Additional venous blood draws from peripheral sites (e.g. antecubital, radial vein) may be required if the arterial and central line catheters have been removed before the conclusion of 48-hour study period, heparinized, or would be compromised by extra blood draws. Blood draw volumes will be approximately 20 mL.

The toxicity of Vitamin C is very low; therefore, potential benefit far outweighs known risks.

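### The lost-access rule counts an arterial line as acceptable central venous access without saying what the access is for, and it conflicts with the dosing-completion list on when infusions stop

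*Combined protocol and SAP*

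**What the plan says.** Wherever the protocol names a route for this trial's drug, it is intravenous. Study Design describes a trial "comparing high-dose intravenous vitamin C to placebo (normal saline) infusions", the dose paragraph in that section says "intravenous Vitamin C will be given as 200mg/kg/day divided over 4 intravenous doses", and Intervention and Controls says "This is a two-arm trial comparing high-dose IV vitamin C to normal saline placebo controls".

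Two places tie the stopping of study drug to vascular access:

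- **Study Design, completion of study drug administration.** Dosing ends at the first of several listed events. The item on access (numbered 3) reads "Inability to obtain peripheral access after removal of central line".
- **Glucose Monitoring Plan.** "If subject loses central venous access (PICC line and arterial line acceptable), Vitamin C infusions are to stop but subject not withdrawn". Data collection then continues to the end of the study.

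Two places describe access for blood:

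- **Glucose Monitoring Plan**, in the same bullet list: "To accommodate the required glucose monitoring via the metabolic lab, each subject will have a dedicated peripheral line".
- **Ethical Considerations**: "The blood draws will be done, when possible, from in-dwelling arterial line and central line catheters". Peripheral venous draws are allowed if those catheters come out before the 48-hour period ends.

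Under Outcomes, enrollment goal 4 is that all 24 patients receive all their scheduled doses.

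**The concern.** The lost-access sentence has one operative consequence for dosing: infusions stop or they do not. It makes that depend on central venous access, and then lists as acceptable a line that is not venous. The purpose of the access is left unstated, so unit staff cannot tell from the protocol whether the parenthesis concerns where drug may go or where blood may be taken.

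Two things are at stake. The first is safety: ICU and stepdown nurses give the bags, and wording that links an arterial line to continuing an infusion should not depend on each reader guessing the intent. The second is the pilot's own feasibility measure. If two sections stop dosing under different conditions, the number of patients who received all their doses depends on which section the unit followed.

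**Working it through.** No figure in the plan bears on this point, so the check sets the passages side by side.

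**Step 1. What the parenthesis could mean.** Take a patient whose central venous line is out and who still has an arterial line.

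- *Infusion reading* (the listed lines are acceptable for giving drug): the arterial line counts, the stop is not triggered, and infusions continue. This sits against the intravenous route in Study Design and in Intervention and Controls.
- *Sampling reading* (the listed lines are acceptable for drawing blood): the arterial line again counts, the stop is not triggered, and infusions continue through some venous line that the sentence does not name.

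Both readings let infusions continue. They differ in which line may carry the drug, not in how many doses are given.

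**Step 2. Does the sampling reading settle it?** It fits the sentence's place in the glucose plan and the use of arterial lines in Ethical Considerations. But the same bullet list already gives each subject a dedicated peripheral line for laboratory glucose, and Ethical Considerations allows peripheral draws. Loss of central access would then not by itself end sampling, and the reason for stopping infusions is left unexplained. Neither reading fits all the text.

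**Step 3. The two stopping rules compared.** In every row the central venous line is out and there is no PICC line.

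| Arterial line remains | Peripheral access obtainable | Glucose Monitoring Plan | Completion list, item 3 |
|---|---|---|---|
| Yes | Yes | not stopped | not stopped |
| Yes | No | not stopped | stopped |
| No | Yes | stopped | not stopped |
| No | No | stopped | stopped |

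The rules disagree in two of the four states, and in opposite directions. In the second row, the glucose plan taken alone leaves infusions running when no venous access is available. In the third row, it stops a patient whom the completion list, by implication, would keep on drug through peripheral access.

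**Step 4. Effect on the dosing goal.** The goal is 24/24. One patient in a disagreeing state who is stopped under one rule but not the other moves the count between 24/24 and 23/24 (23 ÷ 24 = 95.8%). The plan does not say whether doses withheld under a stopping rule count as missed.

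**The case against.** The strongest defence is that the sentence is a stopping condition and never names the arterial line as a route for drug. It sits among bullets on laboratory glucose, and Ethical Considerations pairs arterial and central lines for blood draws. Read as sampling access, it does not contradict the intravenous route. Nothing shows that the electronic record prompt carries this wording, so the hazard is inferred, not documented. All of that stands. A reader might infer that the protocol permits intra-arterial infusion; the documents do not support that.

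A reader might also infer that a definite number of doses turns on the infusion-or-sampling question. That does not follow either: when an arterial line remains, neither reading triggers the stop (step 1). Differences in doses given come from the conflict with the completion list.

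Nor is this sentence the sole access-based instruction on continuing or stopping, since completion item 3 is another. It could be argued that the two rules simply add up, with dosing ending when either is met. The protocol does not say so: the completion list sets out its own conditions and does not include loss of central access.

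What the defence does not remove is the unstated purpose of the access, the listing of an arterial line under central venous access, and the disagreement between the two sections.

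**Conclusion.** The point holds as an ambiguity and an internal conflict in a stated rule. The Glucose Monitoring Plan sentence does not say what the access is for, and read literally it leaves infusions running when only an arterial line remains. It also disagrees with completion item 3 in two of the four access states compared, which makes the 24/24 dosing goal unclear.

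The size cannot be given in patients. The documents contain no line-removal times, although Ethical Considerations expects that lines may come out within 48 hours. The conclusion assumes that item 3 implies dosing may continue when peripheral access is obtained, and that an arterial line alone does not count as peripheral access under that item. It takes no view on which route or stopping rule is right.

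**What to change.** Reconcile the lost-access sentence in the Glucose Monitoring Plan with the intravenous route in Study Design and Intervention and Controls, with completion item 3, and with the blood-draw text in Ethical Considerations:

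1. Replace the sentence with two rules: one naming the access that governs continuing or stopping study drug, and one naming the access from which glucose and study blood may be drawn.
2. Put the arterial line only under the rule it was meant for.
3. Make the first rule and completion item 3 the same rule in the same words.
4. Use that wording in the electronic record prompt and the in-service training.
5. State whether doses withheld under the rule count against enrollment goal 4.

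The investigators decide the clinical content. The cost is a short amendment and matching training text, with no extra patients, samples or procedures.

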Our targeted lipidomic analysis will examine a specific subset of lipids identified alterations in the arachidonic acid metabolite pathway associated with inflammation and coagulopathy. We will track patient condition before, during, and after CPB by mass spectrometric profiles of selected biolipids with the initial focus on free fatty acids, eicosanoids, 3-PUFA-derived lipid mediators, phospholipid substrates of cPLA2 α (including oxidized forms), and isoprostanes, which are well-characterized markers of oxidative stress and redox status. Lipid entities will be quantitatively determined via LC tandem mass spectrometry.²⁸⁻³⁰

Clinical outcomes: Clinical data will be obtained from the patient's chart under direct supervision of the PI by a research coordinator and/or a graduate student listed in the study personnel. Data will include: (1) Demographics (age, race, ethnicity, gender, height, weight); (2) Pertinent medical history (hypertension, congestive heart failure); (3) Surgery data (cardiac surgeon, date and time of surgery, time and details of bypass, total heparin administered, total protamine administered, blood products administered (type, units),

November 16, 2016

other concomitant medications [times, dosages/amounts]); (4) Surgical complications (e.g. fever, respiratory failure, intubation (Y/N, duration), chest tube drainage amount); (5) Incidence of AF; (6) Hospital outcomes: length of ICU stay, length of step-down and/or floor stay, and patient discharge disposition. Patients will be followed up through hospital discharge or in-hospital death.

POST-RANDOMIZATION TREATMENT

All clinically-indicated treatments (including blood product, medications, and fluid administration) will be given as appropriate per attending physician discretion.

Study-specific blood samples will be obtained by the anesthesiologist or nursing staff, depending on the patient's location at each time point, at four times:

- 1st Draw: Baseline (after anesthesia induction but prior to drug administration)
- 2nd Draw: Approx. 60 min. after protamine sulfate is administered (during CPB),
- 3rd Draw: 24 hours post-baseline (+/- 2 hours),
- 4th Draw: 48 hours post-baseline (+/- 2 hours).

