2. Any clinically important, untoward medical occurrence that is thought to be associated with the study drug or procedures, regardless of the “expectedness” of the event for the course of a patient undergoing cardiac bypass surgery.
3. Investigators will report all *serious, unexpected, AND study-related* adverse events from the time of informed consent through study hour 48 that are considered to be harmful and unintended responses to the investigational product and/or study related procedures in the participants’ case report forms. ‘Responses to investigational product’ means that the causal relationship between an investigational product and an adverse event cannot be ruled out.

The following will be reported as adverse events:

Investigators will report all unanticipated problems that **involve risk or harm to a research participant AND was not anticipated or foreseen (e.g., not described in the consent form) AND is probably or definitely related to or caused by the research** to the sponsor/IND Holder by phone and email within 24 hours of becoming aware of event. The Institutional Review Board will be notified within 5 business days of receiving notice of the unanticipated problem.

The study team will report all unanticipated problems, defined as problems that **involve risk or harm to a research participant AND was not anticipated or foreseen (e.g., not described in the consent form) AND is probably or definitely related to or caused by the research**, to the DSMB within 7 calendar days of the Sponsor/IND Holder being notified of the event.

The DSMB will also determine if the serious adverse event is unexpected for Vitamin C. If the DSMB determines that any serious and study-related adverse event is unexpected for Vitamin C, the FDA will be notified within 7 calendar days. Such events may also meet the definition of *Unanticipated Problems* as described below.

Investigators must report *Unanticipated Problems*, regardless of severity, associated with the study drug or study procedures within 24 hours. An unanticipated problem is defined as follows:

Any incident, experience, or outcome that meets all of the following criteria will be reported from the time of consent through study hour 48 until resolved, withdrawn from the study, death occurs or lost to follow up:

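### Systematic adverse-event checks stop at study hour 48, at or about 6 hours after the last scheduled dose, although patients are followed to discharge and other reporting clauses carry no cut-off

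*Combined protocol and SAP*

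**What the plan says.** The section on adverse event and safety reporting sets the ascertainment window: "Investigators will determine daily if any clinical adverse experiences occur during the period from informed consent through study hour 48". Events found in that window "will be followed up through resolution, resolved with sequelae, unresolvable or death". Two further clauses repeat the limit. Item 3 of the reportable-event list covers serious, unexpected and study-related "adverse events from the time of informed consent through study hour 48 that are considered to be harmful and unintended responses". The definition of an unanticipated problem says that qualifying incidents "will be reported from the time of consent through study hour 48 until resolved, withdrawn from the study, death occurs or lost to follow up".

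Other clauses in the same section state no hour. Item 1 of the list (events outside the expected course of bypass surgery) has none, nor does item 2: "Any clinically important, untoward medical occurrence that is thought to be associated with the study drug or procedures". The duties to notify the sponsor/IND holder, the IRB and the DSMB run from awareness or notification of the event and set no limit on when it began.

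On dosing, the completion rule under Study Design lists "Final drug dose at 48 hours". The dose paragraph just before it, and the section on intervention and controls, describe four doses a day at six-hour intervals for two days, in 50 mL bags, about 400 mL in all.

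The glucose monitoring plan adds: "Point of care glucose testing may resume 36 hours after the last infusion of study drug". Under clinical outcomes, "Patients will be followed up through hospital discharge or in-hospital death".

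**The concern.** A drug-safety window would normally extend some way past the last exposure. Here it closes at or shortly after the last scheduled dose, while the protocol itself treats the drug as able to distort meter readings for a further 36 hours and warns about insulin decisions based on such readings. Patients remain under study follow-up during that time, so the short window is not forced by loss of contact.

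The trial-management section allows the trial to be stopped for adverse effects, a DSMB oversees safety, and the pilot is meant to inform a larger trial, including possible changes to dose loads and schedules. All of these depend on events being captured consistently. Chart review afterwards could recover some later events, but not a judgement of relatedness made at the time and under blinding.

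**Working it through.** **Dosing end, from the protocol's own figures.** Inputs: 4 doses per day, 2 days, 6-hour intervals, 50 mL per bag, 200 mg/kg/day.

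- Number of doses: 4 × 2 = 8.
- Volume: 8 × 50 mL = 400 mL, which reproduces the stated total.
- Dose times with the first dose at hour 0: 0, 6, 12, 18, 24, 30, 36, 42.
- A dose at hour 48 would be the ninth. Volume: 9 × 50 mL = 450 mL, which does not match 400 mL. Amount: 200/4 = 50 mg/kg per dose, so 9 × 50 = 450 mg/kg against 8 × 50 = 400 mg/kg.

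The completion rule and the schedule therefore disagree. Both are carried forward; which is right is not judged here.

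**Adverse-event window after the last dose** (48 minus the hour of the last dose):

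- last dose at hour 48: 48 − 48 = 0 h;
- last dose at hour 42: 48 − 42 = 6 h.

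**Glucose precaution against the window** (hour of last dose + 36, then minus 48):

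- last dose at hour 48: 48 + 36 = 84; 84 − 48 = 36 h after the window closes;
- last dose at hour 42: 42 + 36 = 78; 78 − 48 = 30 h after the window closes.

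**Early stopping.** A patient whose last infusion is at hour 12 has 12 + 36 = 48, so all 36 hours lie inside the window. The 30 to 36 h figure thus applies only to completers.

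**Hour 0.** It is not defined. Baseline is the natural reading, because the 24 h and 48 h blood draws are timed from it and the baseline draw precedes the first dose. On the eight-dose schedule, placing hour 0 *h* hours after the first dose would give 6 + *h* hours of post-dose window; placing it *h* hours before would give 6 − *h*. Times are counted from the start of each infusion because the protocol gives no infusion duration.

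**What can still catch a new event after hour 48.**

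| Route | Time limit as written |
|---|---|
| Daily adverse-event check | hour 48 |
| Reportable events, item 3 | hour 48 |
| Unanticipated-problem definition | hour 48 |
| Reportable events, items 1 and 2 | none |
| Notification duties to sponsor/IND holder, IRB, DSMB | none on onset |
| Chart outcomes: surgical complications, AF, stay, disposition, in-hospital death | discharge or in-hospital death |

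The chart outcomes name no glucose-related or renal event. Creatinine is to be followed with no stated end, and urine sampling ends at 24 h. Items 1 and 2 say what is reportable but schedule no one to look for it.

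**The case against.** A reader might infer that harms after the last infusion go unrecorded. The documents do not support that. AF, surgical complications, disposition and in-hospital death are collected to discharge, events that began by hour 48 are followed to their outcome, and items 1 and 2 and the notification duties have no hour limit. For the same reason it cannot be said that a late event falls outside all reporting.

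A reader might also treat the 36 hours as a general carry-over period and place renal events in it. The protocol ties that figure only to point-of-care glucose testing, and it links renal calculi to infusions or intake over days to weeks. Nor does the gap apply to every patient: half of the planned 24 receive saline and have no vitamin C interference, and patients who stop early may be fully covered.

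The glucose hazard has safeguards of its own: signage, a ban on point-of-care testing, laboratory confirmation before insulin, study staff who monitor insulin use, and exclusion of known diabetes. A breach would be a protocol deviation, and deviation reporting has no hour limit.

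All of this stands and limits the size of the point. It does not remove it. The safeguards aim to prevent the error; they do not provide for finding its consequences. No scheduled adverse-event check is planned after hour 48, and clauses with and without a cut-off sit side by side in one section.

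**Conclusion.** The point holds in a limited form. Systematic ascertainment, item 3 reporting and the unanticipated-problem definition end at study hour 48, which is 0 h or about 6 h after the last dose, depending on which dosing statement applies. For vitamin C patients who complete dosing (at most the 12 planned for that arm, if 24 complete), 30 to 36 h of the 36 h glucose-meter precaution lie beyond the window. New events after hour 48 are caught only if they match a listed chart outcome or someone reports them under an untimed clause. The section is therefore also inconsistent about its cut-off.

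The figures assume that hour 0 is baseline, that the first dose is given then, and that the interval is exactly six hours. The point is a should-fix: part of the capture already exists, and the correction is small.

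**What to change.** Define study hour 0. In the daily ascertainment sentence, in item 3 and in the unanticipated-problem definition, replace the hour-48 limit with hospital discharge or in-hospital death, and state that the same cut-off governs items 1 and 2 and the notification duties. Separately, reconcile the completion rule's final-dose time with the eight-dose, 400 mL schedule.

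The cost is a wording change, a few more days of adverse-event checks in inpatients who are already followed, and slightly more events to log. No contact after discharge is needed. The price of that choice is that a patient discharged less than 36 h after the last infusion would have the remaining hours uncovered, which is acceptable for a pilot whose follow-up ends at discharge.
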